#### **Overall Rationale and Organization**

These clinical pharmacokinetic-pharmacodynamic experiments aim to establish  $\alpha 4\beta 2^{*}$  nAChRs as appropriate targets for treatment of levodopa resistant gait and balance deficits in hypocholinergic PD subjects. Subjects will be drawn from **Project II** and the **Clinical Resource Core**. In **SA1**, we will use [F]flubatine PET imaging to determine the lowest VCN dose producing high  $\alpha 4\beta 2^{*}$  nAChR occupancy. In **SA2**, we will use this dose to perform pharmacodynamic studies of VCN effects on laboratory measures of gait and postural control. These studies will determine if  $\alpha 4\beta 2^{*}$  nAChR stimulation produces the predicted effects on laboratory measures of balance and gait – directly addressing our central hypothesis. In **SA3**, we will study the effects of subacute VCN administration on a measure of attentional capacity sensitive to cholinergic deficits, testing our hypothesis that improvement in attention capacity will correlate with improvements in gait and postural control. These data will evaluate a likely physiological mechanism mediating the effects of stimulating  $\alpha 4\beta 2^{*}$  nAChRs in the context of the hypocholinergic PD brain, and provide important validation data for the rodent model used in **Project I**.

We propose subacute (days) VCN administration and focus on hypocholinergic PD subjects. Because repeated  $\alpha 4\beta 2^*$  nAChR stimulation, as would be experienced by chronically treated patients, induces functional receptor upregulation, assessing  $\alpha 4\beta 2^*$  nAChR occupancy with a single VCN dose in VCN naïve subjects will be misleading. Moreover, a VCN dose that produces high percent receptor occupancy in a VCN naïve subject may exhibit considerably less  $\alpha 4\beta 2^*$  nAChR occupancy in subjects exposed repeatedly to VCN and with  $\alpha 4\beta 2^*$  nAChR upregulation. It might be scientifically interesting to include normocholinergic PD subjects, but safety concerns hinder this approach. In our model (**Overview; Project I** data), dopaminergic striatal deficits result in compensatory "loading" of other brain systems. Normocholinergic PD subjects depend on increased cholinergic neurotransmission to compensate for striatal dysfunction, placing them at increased risk of adverse events resulting from reduced cholinergic signaling (32,46). VCN is a partial agonist with an efficacy of approximately 40% of ACh. In normal individuals, VCN produces measurable improvements on cognitive tests

(79,88), but in normocholinergic PD subjects, VCN may interfere sufficiently with  $\alpha 4\beta 2^*$  nAChR mediated compensation to produce functional impairments, including cognitive impairment and/or diminished balance, including damaging falls. It is not feasible to recruit sufficient subjects to do these experiments in an inpatient setting, which would be required to mitigate these potential side effects. For these reasons, we will not expose normocholinergic PD subjects to VCN. Beyond these important safety concerns, adding study groups to the proposed experiments would reduce statistical power for a fixed sample size, increasing the Ns required for a valid study beyond that which can be supported by funds available for Udall Center studies.

We will investigate the possibility that regulation of  $\alpha 4\beta 2^*$  nAChRsmight be different in PD brain versus brains of normal individuals. We will investigate this possibility with a focused study of  $\alpha 4\beta 2^*$  nAChR receptor occupancy in a small group of normal subjects. Following the conclusion of receptor occupancy studies in hypocholinergic PD subjects, we will perform a more limited, parallel, dose-receptor occupancy study to determine if there are major differences in VCN receptor occupancy between PD and control subjects.

**Subject Selection**: PD subjects will be drawn from **Project II** subjects who have undergone [F]FEOBV imaging to identify cholinergic deficits.

We will study subjects with cortical innervation deficits below the 5th percentile cutoff of controls as defined previously (17). General inclusion and exclusion criteria are specified in the **Clinical** 

**Resource Core** and **Project II**. Current or previous (within last 6 months) use of any product or medication containing nicotinic agents, including use of tobacco products such as cigarettes, cigars, pipes, chewing tobacco, etc., e- cigarettes, OTC nicotine patches, chewing gum containing nicotine, or varenicline is an exclusion. While most data does not indicate that VCN causes suicidality or cardiovascular problems (73 -

81), we will exclude subjects with depression, active cardiovascular disease, history of seizures, or alcohol use disorders. (see **Human Subject Protection**).

The **Clinical Resource Core** and **Project II** project initial enrollment of 95 PD subjects with longitudinal followup of 75 PD subjects. Based on prior results, we project that 30% (32) of the initially enrolled subjects will be hypocholinergic. Based on preliminary data (**Project II**), 25% (20) of the longitudinally followed PD subjects will convert from normo- to hypocholinergic during the project period. This gives a total of 52 eligible subjects (Table 1). Our long-standing experience is that a significant fraction of subjects participate in multiple experiments, so we anticipate little difficulty in recruiting the projected 55 PD subject-equivalents required. In our recently concluded Program Project Grant (NS15655), we studied 151 PD subjects. All underwent at least 2 PET studies with 112 undergoing 3 or more scans (69 - 3 studies; 43 - 4 studies). We are basing our estimates on a stringent 5th percentile cut-off relative to our normal control database. We will carefully monitor subject recruitment to enroll the target number of hypocholinergic PD subjects. If needed, **Core B** will preferentially recruit an enriched sample of PD subjects with longer duration disease and/or mild cognitive changes, subjects more likely to exhibit cholinergic deficits. **Core B** will be aided in recruitment by the **Core D** (Education and Outreach Core). **Appendix 1** contains a detailed schedule of study activities.

**IND Exemption:** We obtained an IND exemption from the FDA.

**Specific Aim 1:** To use [F]flubatine PET to assess VCN occupancy of brain  $\alpha 4\beta 2^*$  nAChRs after subacute VCN administration to the subgroup of PD subjects with cholinergic deficits.

Rationale and Predictions: We will use [F]flubatine PET to select an appropriate VCN dose for **SA2** and **SA3** studies. Application of [F]flubatine PET will allow selection of the lowest dose producing high (>90%) receptor occupancy. Measuring VCN displacement of [F]flubatine obviates the need for clinical dose escalation studies in hypocholinergic PD subjects.  $\alpha 4\beta 2^*$  nAChRs are complex heteromeric proteins with highly regulated expression and function. These studies are essential, as the PD brain is a very different environment from a normal brain. We predict that that these studies will identify a VCN dose at the lower end of the clinically used range producing high (>90%)  $\alpha 4\beta 2^*$  nAChR occupancy. A recent acute VCN dose study in acutely abstinent smokers (upregulated  $\alpha 4\beta 2^*$  nAChRs) with [F]FA-85380 reported that a single 0.5 mg

[figure not shown]

Figure 3: [F]flubatine PET. Left Panel: averaged late frame images of a control subject. High binding in thalamus, striatum, cerebellum, and frontal cortex. Right Panel: Typical time-activity curve for a control

oral VCN dose (typical treatment dose = 1 mg bid) produced ~95% receptor occupancy with imaging several hours after ingestion (70). This result suggests strongly that lower clinical VCN doses will produce high (>90%) receptor occupancy. All subjects will undergo baseline [F]flubatine scanning after subacute VCN treatment to induce upregulation and following VCN washout to allow measurement of per cent VCN occupancy of upregulated  $\alpha 4\beta 2^*$  nAChRs.

*Preliminary Data:* Our PET Center is performing [F]flubatine imaging on a routine basis (**Figure 3, Table 2**). [F]flubatine PET has regional distribution expected for α4β2\* nAChRs, excellent signal to noise properties, and imaging can be completed in 90 minutes. Notably, regional binding values are highly reproducible across subjects with low coefficients of variation (**Table 2**). *Procedures:* α4β2\*

Table	2:	[  F]Flubati	ine bind	ing val	ues	for	regions
express	sing	g high levels	s of α4β2	nAChF	ls. N	= 3	controls.
DVR =	: C	Distribution	Volume	Ratio;	SD	=	Standard
Deviation; COV = Coefficient of Variation.							

Region	Mean DVR	SD	COV
Thalamus	1.57	0.11	6.9%
Striatum	0.90	0.02	2.1%

nAChR expression will be measured in vivo with [F]flubatine. Subjects will receive varying VCN doses. [F]Flubatine imaging will be done 10 days after initiation of VCN administration and 5 days after VCN discontinuation (**Figure 4**). The difference between [F]flubatine binding before and after VCN discontinuation will be measured to assess  $\alpha 4\beta 2^*$  nAChR occupancy. Receptor occupancy will be assessed in regions exhibiting high  $\alpha 4\beta 2^*$  nAChR expression; thalamus, striatum, and cerebellum, as results are likely to be more variable in regions with lower  $\alpha 4\beta 2^*$  nAChR expression. Based on prior animal and human studies, 7-10 days

is adequate to induce receptor upregulation (91-95). VCN has a  $t_{1/2}$  of ~24 hours and 10 days will be adequate to attain equilibrium and induce upregulation. VCN pharmacokinetics (PK) do not change with age and absorption is unaffected by food (96). Five days is adequate to clear VCN.  $T_{max}$  is 2-4 hours post oral administration. The first scan will occur in the afternoon of day 10 after the morning VCN dose to avoid peak dose effects which could increase variance.

The recommended clinical VCN dose schedule is 0.5 mg per day for 3 days, followed by 0.5 mg bid for 4 days, followed by 1 mg bid. Mocking et al. recently reported positive neuropsychological results of subacute VCN

treatment (0.5 mg/day for 3 days, then 1 mg/day for 4 days) in normal controls (79). Because we are administering VCN to a clinical population and not young, healthy controls, we propose lower initial doses than Mocking et al. We will start with 0.25 mg/day on a subacute treatment schedule of 10 treatment days. A potential acute side effect of VCN is nausea, though this is unusual in non-smokers with doses below 1 mg per day. To reduce the chance of nausea or other side-effects, we will use a series of escalating dose schedules (**Appendix 2**). VCN will be prepared by the U-M Health System Research Pharmacy. VCN pills are small, easily encapsulated in gelatin capsules, and will be dispensed in blister packs to facilitate administration and compliance monitoring. The initial maximum dose studied will be 0.25 mg/day. Subsequent, projected maximum doses are 0.25 po bid, 0.5 mg po bid, and 1 mg po bid (if needed). Twice daily dosing is used to minimize peak dose effects. We anticipate 3 dose points, each consisting of 3 participants (total of 9

Figure 4: Timeline of SA1 Experiment

participants), to establish the required oral dose for **SA2** and **SA3** experiments. The results of the initial (0.25 mg/day maximum dose) study will be used to select the next dose point. If there is a substantial effect on [F]flubatine binding (>50% reduction), we will use the 0.25 mg bid maximum dose schedule for the next experiment. If the effect on [F]flubatine binding is <50% reduction, we will use 0.5 mg bid maximum dose schedule for the next experiment. Selection of the subsequent dose schedule will be based on the results of

the 0.5 mg bid maximum dose experiment. We will increment dose schedules until there is no additional reduction in [F]flubatine binding, i.e., remaining binding is non-specific binding, and the penultimate maximum dose defines our **SA2-SA3** study dose. Based on the work of Lotfipour et al., who found that a single oral 0.5

mg VCN dose produced ~100% receptor occupancy (70), we don't anticipate using the highest (1 mg po bid) dose schedule). We will measure plasma VCN levels at the time of the initial scan (Pharmacokinetics Core, U- M College of Pharmacy; see attached letter from [name], Core Director). These measurements are not for formal PK studies as VCN PK is well established, but rather to confirm study drug compliance. We aim to establish the lowest dose producing high ~100%) receptor occupancy and if we achieve this goal after studying 2 dose schedules (6 participants total), we will stop and proceed to **SA2** experiments.

PD Subjects will continue their customary PD treatments. Subjects will be evaluated in the University of Michigan Functional Neuroimaging, Cognitive and Mobility Laboratory (see Facilities & Resources). All subjects will undergo a standard clinical and brief psychometric evaluation immediately prior to VCN treatment initiation, at the time of initial scan and at the time of the second scan. Subjects will undergo a MDS-UPDRS, Geriatric Depression Scale, Montreal Cognitive Assessment, WAIS Digit Span and Digit Symbol coding tests, and D-KEFS executive function/working memory tests. Subjects will be screened for suicidality with the Columbia Suicide Severity Rating Scale (C-SSRS; http://www.cssrs.columbia.edu/) before VCN treatment and at the time of each PET study. [name] is certified in use of the C-SSRS (Appendix 3) and [name] and other relevant members of the Clinical Resource Core will also become certified. Subjects will be directly observed for 3 hours after their initial VCN dose, with phone follow-up the next day and weekly thereafter. Subjects will be screened for history of seizures and alcohol abuse. The latter will be assessed with the WHO Alcohol Use Disorder Identification Test (AUDIT). Per the WHO guidelines, individuals with scores >8 (ages 18-65) or >7 (ages >65) will be excluded. Individuals with a history of seizures will be excluded. Participants will be advised to refrain from alcohol use during study participation. An investigator ([name] or [name]) will be on-call for subject concerns at all times. Data will be recorded on standard CRFs and entered into the database for management and analysis by the **Biostatistics and Data Management Core**. Adverse events will be classified by organ system and assessed for causality. All potential possible adverse events will be discussed by the Udall Center Executive Committee acting as DSMB, and reported promptly to the IRB and NINDS.\

Following completion of the PD subject study experiment 1, we will perform a limited experiment to assess  $\alpha 4\beta 2^*$  nAChR occupancy in age-matched controls. Controls will receive VCN (no placebo) for 10 days. We will select a subset of the doses used for the PD subjects in experiment 1 to assess receptor occupancy in normal controls. Assuming we don't detect very high (>90%) occupancy with our initial dose (0.25 mg/day), we will expose controls to one of three different dosages of varenicline to construct a dose-occupancy relationship for comparison with the results in PD subjects. Based on the results of experiment 1, experiment 2 will include the following dosages

with a goal of 3 patients per cohort: .25mg QD, .25mg BID and .5mg BID. All procedures will be identical to experiment 1. Control subjects will be drawn from the normal control pool characterized concurrently in the Clinical Core of the Udall project, much as the PD subjects are drawn from the pool of PD subjects. Control subjects will also be recruited from the UM Health Research website if needed. We anticipate studying 9 subjects, 3 at each dosage point. To adjust for potential dropouts, we will budget 12 control subjects.

Potential Problems and Alternatives: The results of Loftipour et al. suggest that low doses will produce high  $\alpha 4\beta 2^*$  nAChR occupancy (70). Commercially available VCN pills are small and division beyond bisection is likely to be inaccurate. 0.25 mg/day is the lowest feasible dose and if we find this dose produces high per cent receptor occupancy, no further testing will be necessary. VCN tolerability may be a problem as this agent has not been tried specifically in PD subjects previously. To avoid any problems, we are starting with low doses and using an incrementing schedule. Nausea was infrequent in a recent trial in AD which used significantly higher doses (89). If tolerability is an issue, then we will alter the incrementing schedule to more gradually "ramp" up to the desired dose.

**Specific Aim 2:** To assess the effects of pharmacologic  $\alpha 4\beta 2^*$  nAChR activation on laboratory measures of gait function and postural control in PD subjects with cholinergic deficits.

*Rationale and Predictions:* The central hypothesis of this project is that deficient activation of  $\alpha 4\beta 2^*$  nAChRs consequent to the degeneration of cholinergic projections causes balance and gait abnormalities in PD.

Consequently, restoration of  $\alpha 4\beta 2^*$  nAChR stimulation should improve these deficits. In this target engagement pharmacodynamic experiment, we will evaluate the effects of the  $\alpha 4\beta 2^*$  nAChR partial agonist VCN on laboratory measures of gait function and postural control in hypocholinergic PD subjects. We predict that subacute VCN administration will improve gait function and postural control in hypocholinergic PD subjects. We chose a pair of relevant physiologic endpoints; gait speed and Horak's JERK (97,98,99). Slow gait is a cardinal sign of PD and we demonstrated recently that slowed gait is strongly associated with neocortical cholinergic denervation (56). Similarly, Rochester et al. found that gait speed in PD correlated with

an indirect clinical electrophysiologic measure of cortical cholinergic function (100). Slowed gait is also a feature of our combined dopaminergic-cholinergic rat model (32). We will apply the Instrumented test of postural Sway (ISway; APDM Mobility Lab; http://apdm.com/gait-and-posture/Mobility-Lab/index.html), a relatively simple and robust method for evaluating postural control with a belt-worn inertial sensor (97,98,99). ISway was developed specifically to assess postural control in PD subjects and is validated against more complex methods. Abnormalities of these types of measures are associated in both cross-sectional and prospective studies with increased fall risk in the elderly, and measure relevant postural control phenomena in

PD (101-104). JERK is one of several parameters measured by ISway, captures postural sway irregularity, and possesses strong validity, good test-retest behavior, and good correlation with UPDRS III PIGD scores (97).

*Preliminary Data:* Our group implemented the ISway system in the Functional Neuroimaging, Cognitive and Mobility Laboratory (**Table 2**). We studied 11 similar PD subjects, 6 with a history of falls and 5 without any fall history. ISway measures of postural control differentiated fallers and non-fallers (**Table 2**).

*Procedures*: The **SA1** experiment will select the VCN dose. Based on discussions with the proposed **Biostatistical and Data Management** co-Core leaders, we will employ a randomized double- blind, placebocontrolled, 2-period, 2-sequence crossover design to assess the effects of subacute VCN administration on gait function, postural control, and attention in PD subjects with cholinergic deficits (**Figure 5**). PD participants will be on stable doses of dopaminergic therapy for 3 months prior to enrollment and continue on their usual Table 3: ISway: data in non-fallers (n=5) and falling PD (n=6). Means +SD.

	Non- Faller	Faller	t-test (p- value)
Jerk	0.082 ±	0.213±	t = -2.0
	0.080	0.125	(0.072)
RMS	0.058±	0.109±	t = -2.3
	0.021	0.045	(0.045)
Velocity	0.114±	0.200±	t =-2.3
	0.050	0.067	(0.049)
Centroid Freq (AP)	0.734±	0.617±	t=2.7,
(AP)	0.160	0.140	(0.026)

schedule of dopaminergic medications for the duration of this study. Individuals with depression and unstable cardiac disease will be excluded. Within-subjects crossover designs were employed successfully in recent VCN trials for AD and mood disorders during smoking cessation (89,90).

We will administer VCN or placebo for 3 weeks, followed by a 3 week washout period, and crossover to placebo or VCN for the 3 week second treatment period. Study visits will be completed within a five business day window before or after the target date. The duration of the treatment and washout periods is based partly on prior human experimental and trial experience (89-95). Mocking et al. detected improved cognitive effects of VCN with a week of treatment (79). We chose a longer period to ensure stable receptor upregulation and because initiation of treatment may require gradual dose incrementing. The washout period is based partly on work by Zhang et al. with another  $\alpha 4\beta 2^*$  nAChR partial agonist in MPTP lesioned non-human primates (71). This group reported an effect of

ABT-089 on levodopa induced dyskinesias close to 2 weeks after dose cessation, well beyond the t1/2 of this agent. This wash-out interval was used also in the recent VCN AD trial (89). The randomization schedule and process will be prepared by the **Biostatistics and Data Management Core.** Blinded, encapsulated study drug (VCN and placebo) will be supplied by the U-M Research Pharmacy to the study coordinator. The latter will dispense the study medication. Subjects will be evaluated in the University of Michigan Functional Neuroimaging, Cognitive and Mobility Laboratory (see **Facilities and Resources**). Subjects will be directly observed for 3 hours after initial VCN dose and with phone follow-up calls 1-2 business days after starting the medication treatment period, and weekly thereafter. Follow-up phone calls will be completed within a two business day window before or after the target date. VCN plasma levels will be evaluated at end of both treatment periods on days 22 and 64 through a blood draw to monitor compliance. Blood samples will be stored at the University of Michigan Functional Neuroimaging, Cognitive & Mobility Laboratory until the study is finished. Data will be recorded on standard eCRFs and entered into the database for management and analysis by the **Biostatistics and Data Management Core.** Adverse events will be classified by organ system and assessed for causality. All potential possible adverse events will be discussed by the Executive Committee, and reported promptly to the IRB and NINDS.

Gait speed and postural control will be assessed at baseline, at the end of the first VCN/placebo administration period, at the end of the washout period, and at the end of the second VCN/placebo administration period. Gait and postural control will assessed by the **Clinical Resource Core (Core B)** using the Mobility Lab system that is already established (see Table 3; methodology for Mobility Lab will be as described in detail in Project II). MDS-UPDRS, Geriatric Depression Scale, Montreal Cognitive Assessment, WAIS Digit Span and Digit Symbol coding tests, and D-KEFS executive function/working memory tests will be administered as part of the evaluations. Subjects will be screened for suicidality with the C-SSRS before VCN treatment, weekly during phone follow-up, and at the end of treatment-washout periods.

[figure not shown]

Figure 5: Schematic Timeline for Experiment 3

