#### Standard Methods:

#### MRI and VMAT2 PET Imaging, Standard PET Methods and Image Processing: See Clinical Resource

**Core**. Flubatine PET Imaging: [18F]Flubatine will be prepared in high radiochemical purity (>95%) with a method developed by our group (68). PET scans will be acquired using a protocol consisting of 18 frames acquired over 90 min following bolus injections of 8 mCi [F]flubatine. Individual image frames within each scan will be corregistered to frame 10 (10-15 min post-injection) to account for patient motion.Full kinetic

modeling requires arterial blood sampling and >two hours of imaging, impractical for this patient population and we will use simpler analyses. Our primary analysis will use an average of the 70-90 min scan data, when tissue TACs are relatively constant, approaching equilibrium (Figure 3). Venous blood samples will be drawn at 70 and 90 min, plasma extracted and counted in a Nal well-counter. Plasma metabolites will be assessed to determine the radioactivity concentration of authentic flubatine. Radiotracer binding measures will be obtained by normalizing the PET tissue concentrations to the authentic venous plasma radiotracer concentration averaged over the 70 and 90 min samples. This measure of tracer binding approximates the total tissue volume of distribution relative to plasma,  $V_{\rm T}$ . This method is well suited to quantification of flubatine binding as flubatine undergoes minimal catabolism, has only moderate plasma protein binding, and equilibrates instantaneously between blood and plasma (116). A secondary analysis will use the simplified reference tissue model (sRTM) (117). SRTM assumes a reference tissue devoid of specific binding sites, used in lieu of an arterial plasma input function to estimate tissue binding potentials. Since no gray matter tissue is devoid of specific binding sites for flubatine, we will test white matter as a reference tissue. White matter reference regions will be defined on co-registered MR volumes, and segmented with FreeSurfer to produce white matter masks. Binary masks, smoothed to PET resolution with white matter defined by all brain voxels with a mask value >0.9 after smoothing, will assure that reference region voxels have >90% contribution from white matter.

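### Aim 1: five days clears varenicline from plasma but probably not from near-saturated receptors, and the plan has no occupancy formula or second-scan assay to correct for it

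*Protocol*

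**What the plan says.** In the Protocol, Specific Aim 1, Procedures, each participant has two flubatine scans: one on day 10 of VCN and one five days after stopping. No pre-treatment flubatine scan is described. The Rationale explains that the second scan is made "following VCN washout to allow measurement of per cent VCN occupancy of upregulated" receptors, so it serves as the unoccupied reference.

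The Procedures support the timing with a half-life of about "24 hours and 10 days will be adequate to attain equilibrium and induce upregulation", and then state: "Five days is adequate to clear VCN".

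On measurement:
- The Procedures say the difference in flubatine "binding before and after VCN discontinuation will be measured to assess" occupancy. No equation follows.
- Standard Methods (Flubatine PET Imaging) makes the primary binding measure a tissue-to-plasma ratio that approximates total V_T, so it includes non-displaceable uptake. White matter is only to be tested as a reference tissue, in a secondary analysis.
- On VCN itself: "We will measure plasma VCN levels at the time of the initial scan". The stated purpose is to confirm compliance. No VCN assay is described at the second scan, although the scan method provides that "Venous blood samples will be drawn at 70 and 90 min".

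On expected occupancy, the Rationale reports that a single 0.5 mg "oral VCN dose (typical treatment dose = 1 mg bid) produced ~95% receptor occupancy with imaging several hours after ingestion (70"), while the Procedures report from the same source that a single oral 0.5 "mg VCN dose produced ~100% receptor occupancy (70"). The target is above 90%. After the first dose level (0.25 mg/day), a 50% reduction in binding decides which schedule is studied next.

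**The concern.** Five half-lives is a rule for plasma concentration, but the quantity measured here is receptor occupancy. When a drug is present at many times its half-occupancy concentration, cutting the concentration 32-fold does not cut occupancy 32-fold. The higher the on-drug occupancy, the more drug is still bound at the reference scan.

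That scan supplies the denominator for per cent occupancy and one side of the raw difference. If it is treated as VCN-free, occupancy is understated. On some metrics the understatement grows with dose, which makes a dose-occupancy curve hard to read. The 50% step after the first dose level and the comparison of PD participants with controls (Hypothesis 1b) use the same pair of scans. With no second-scan VCN level, the residual cannot be checked against data.

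**Working it through.** **The plan's own figure.** With a half-life of 24 h and a washout of 120 h, the fraction left is f = 2^(-120/24) = 1/32 = 3.1%, so 96.9% is cleared. The statement is right for plasma.

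**Assumptions not in the documents.** One-site competitive binding at equilibrium; brain concentration tracks plasma; linear kinetics; the same receptor number at both scans; 120 h between the two VCN levels.

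**Formulas.** O is on-drug occupancy.
- Concentration relative to half-occupancy: x = O/(1 − O)
- Residual occupancy at scan 2: R = xf/(1 + xf)
- Raw difference, as a fraction of full specific binding: O − R
- Per cent occupancy from specific binding: 1 − (1 − O)/(1 − R), which simplifies to O(1 − f)
- Per cent fall in total V_T: (O − R)/(v + 1 − R), where v is non-displaceable uptake divided by full specific binding

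**Results at f = 1/32**

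| O | x | R | Raw difference | From specific binding |
|---|---|---|---|---|
| 90% | 9 | 22% | 0.68 | 87.2% |
| 95% | 19 | 37% | 0.58 | 92.0% |
| 98.5% | 65.7 | 67% | 0.31 | 95.4% |

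For 95%: xf = 19/32 = 0.594; R = 0.594/1.594 = 0.373; O − R = 0.577; 0.95 × 31/32 = 0.920.

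**Where the raw difference turns.** O − R is largest at x = 1/√f = √32 = 5.66, where O = 5.66/6.66 = 85%. Above that it falls as dose rises.

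**Total V_T at 95% occupancy**

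| v (assumed) | Fall as read | Fall with a clean reference, O/(v + 1) |
|---|---|---|
| 0.1 | 79% | 86% |
| 0.25 | 66% | 76% |
| 0.5 | 0.577/1.127 = 51% | 0.95/1.5 = 63% |
| 1.0 | 35% | 47.5% |

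The reading drops below 50% when v exceeds 2 × 0.577 − 0.627 = 0.53. With a clean reference this would need v above 0.95/0.5 − 1 = 0.90. So for v between about 0.53 and 0.90 the residual drug alone would tip the reading. No document gives v.

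**Range of the residual.** Take x for a single 0.5 mg dose from its assumed occupancy, scale by dose, and multiply by accumulation 1/(1 − 2^(−τ/24)), which is 2.0 for daily and 3.41 for twice-daily dosing. The ranges run over the four listed dose levels, 0.25 mg/day to 1 mg bid.
- Single-dose occupancy 95%: R = 37 to 80%.
- Single-dose occupancy 80%: R = 11 to 46%.
- Single-dose occupancy 99%: R = 76 to 96%.
- Single-dose occupancy 95% with a half-life of 20 h: 21 to 64%; with 30 h: 58 to 91%.

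At the first dose level the base case gives x = 19 × 0.5 × 2.0 = 19, which is the 95% row above.

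**The case against.** The best defence is that the stated target is a per cent occupancy. Computed from specific binding, residual drug shrinks numerator and denominator together, and the shortfall is a constant 1/32. Readings still rise with dose, and above 90% stays detectable: a reading of 90% corresponds to a true 0.90/0.969 = 92.9%. This stands. The protocol, however, never says that it will compute occupancy this way. It names a before-after difference and a measure approximating total V_T.

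The model assumptions are also a fair target. The ~95% figure comes from acutely abstinent smokers given one dose and imaged with another tracer. The residual is therefore an estimate with a wide range.

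A reader might infer more than the documents support:
- **That the 50% rule is crossed in the wrong direction at high occupancy.** At 98.5% occupancy and v = 0.5 the fall in V_T is 38%, but the rule applies only after 0.25 mg/day. In the base case the reading there is 51%, on the intended side unless v exceeds about 0.53.
- **That ~100% can never be read.** The ceiling is 96.9%. The protocol itself describes one cited result as both ~95% and ~100%, so an approximate target is not ruled out.
- **That older participants clear VCN more slowly.** The Procedures state, with a citation, that VCN kinetics do not vary with age. Longer half-lives are sensitivity cases only. On the specific-binding metric, 24 h against 30 h moves a true 95% from 92.0 to 89.1%.
- **That the final dose choice rests wholly on this scan.** Escalation ends when binding shows no further reduction. Read on on-drug scans alone, that rule does not use the washout scan.

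**Conclusion.** The clearance statement is right for plasma but does not justify treating the second scan as VCN-free. On the protocol's half-life and a one-site model, about 22 to 67% of receptors remain occupied there for on-drug occupancy of 90 to 98.5%. At a 24 h half-life, assumed single-dose occupancies of 80 to 99% give about 11 to 96%.

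The size of the error depends on the metric: about 3 points if occupancy is taken from specific binding, but large if the raw difference or the change in total V_T is used, as the text literally describes. The V_T figures also rest on an assumed v.

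The point deserves correction but is not critical to the trial. It bears on the Aim 1 occupancy estimates and the PD-control comparison. It might seem to undermine the efficacy result, but the SAP's scope is VCN against placebo at a dose it already fixes (sections 2.2 and 4.1), so the crossover primary analysis is untouched.

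**What to change.** 1. Replace the clearance sentence with a statement that residual occupancy is expected at the second scan and will be corrected for.
2. Assay VCN in the venous blood already drawn at the second scan, as well as at the first.
3. Write down the occupancy equation as a percentage of specific binding, and say how non-displaceable uptake is removed. One option is a regional occupancy plot: regress the fall in V_T on reference V_T across thalamus, striatum and cerebellum; the slope estimates O(1 − f). Three regions give a thin fit, and equal occupancy and non-displaceable uptake across them must be assumed. Do not use the raw difference or the change in total V_T as occupancy.
4. Divide that ratio by (1 − C2/C1), where C1 and C2 are VCN levels at the two scans. If C2 is missing or below quantification, use the stated half-life. Do this in PD participants and controls alike, and report sensitivity to the half-life.
5. State which measure the 50% and 90% figures refer to, and reconcile the ~95% and ~100% attributed to the same source.

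The cost is one extra assay per occupancy participant (9 PD plus 9 to 12 controls, so 18 to 21 on the protocol's counts) and a short methods paragraph. The assay must quantify about 3% of the on-treatment level. No scan, visit or dosing changes, and the half-life correction can be applied to scans already made.
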